5 EFFICACY AND SAFETY ENDPOINTS

Data for the efficacy endpoints will be recorded on an e-diary. This e-diary consists of a:

- 5-day Weekday Diary (bladder diary, Monday Friday), which is used for a 5-day period to record micturition frequency and incontinence episodes, and
- 2-day Weekend Episodic Diary (Saturday and Sunday), which is used to record micturition frequency, incontinence episodes, (pee) volume measurements, and worst leakage severity.

A valid diary day for:

• "Volumes"

In the 2-day Weekend Episodic Diary, is any e-diary day for which at least one "Pee Volume" greater than 0 mL is recorded with complete date and time.

- "Micturitions"
- In 2-day Weekend Episodic Diary, is any diary day for which at least once "Pee Volume" greater than 0 is recorded.
- In 5-day Week Diary, is any diary day for which the response to the question "Number of times using the toilet during the day/night" is not missing.
 - "Incontinence episodes"
- In 2-day Weekend Episodic Diary, is any diary day for which at least:
 - One micturition ("Pee Volume" >0) and
 - One "Leakage" or "Pee in toilet and Leakage" are recorded.
- In 5-day Week Diary, is any diary day for which:
 - The response to the question "How was your day/night" is not missing.

A valid diary for an analysis visit is a diary with at least 4 valid diary days within that analysis visit window. If for more than 7 days the diary is filled in prior to a visit, only the last 7 days prior to that visit will be used for calculation of the efficacy endpoints.

The number of valid diary days: Count of the valid diary days during the 7-day diary period. Days of visits to the clinic will not be counted as valid diary days.

In the event that in the 2-day Weekend Episodic Diary there are two entries with the same collection date and time but with different times of entry on the device, the last entry (time) will be used for analysis.

For several of the secondary efficacy endpoints, diary data will be classified as either "daytime" or "nighttime", where "daytime" is considered to mean "between waking up in the morning and going to sleep later the same day or next day" and "nighttime" means "between going to sleep on a day and waking up on the same or next day".

Whether an entry into the 5-day Week Diary is done during daytime or nighttime is captured on this diary.

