For entries into the 2-day Weekend Episodic Diary, "daytime" and "nighttime" will be derived from the time the subject went to sleep and the time the subject awakened. These times are entered on this diary by the subject.

The go-to-bed time for Sunday is not captured in the diary. In order to distinguish between daytime and nighttime on Sunday the go-to-sleep time will be imputed as occurring a short time after the second (evening) SBPM was performed: time of second SBPM plus 1 hour. If there is no time entered in the diary for the evening SBPM, then the go-to-sleep time will be imputed as 23:59 (on Sunday).

5.1 **Primary Efficacy Endpoint**

The primary efficacy endpoint is the change from baseline to week 12/EoT in mean number of micturitions per 24 hours in children (5 to <12 years of age).

Number of micturitions per 24 hours is calculated from:

• The response to the questions "Number of times using the toilet during the night" and "Number of times using the toilet during the day" on the 5-day Week Diary,

and

• The number of times a "Pee in toilet" or a "Pee in toilet and leakage" was entered into the 2-day Weekend Episodic Diary.

For a weekend day:

- The daytime micturitions will be derived from the number of times a "Pee in Toilet" or a "Pee in Toilet and Leakage" was entered into the 2-day Weekend Episodic Diary between the time the subject woke up (exclusive) and went to sleep (inclusive).
- The nighttime micturitions will be derived from the number of times a "Pee in Toilet" or a "Pee in Toilet and Leakage" was entered into the 2-day Weekend Episodic Diary between the time the subject went to sleep (exclusive) and woke up (inclusive).

The total number of micturitions per weekend day is equal to the total number of times, in the diary, an amount of pee was recorded during daytime and nighttime for that day.

For each subject, the mean number of micturitions at Visit x (x=4, 5, 6, 7), using all available (non-missing) number of micturitions per 24 hours for the valid days in the diary (at least 4 and maximally 7), will be calculated as:

Sum of the number of micturitions (per 24 hours) over the valid diary days prior to Visit x Number of valid diary days

Note:

- If for a week day (Monday Friday):
 - the number of daytime micturitions is missing but the number of nighttime micturitions is not missing then the number of micturitions for that day is considered to be the number of micturitions during the nighttime.

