- the number of nighttime micturitions is missing but the number of daytime micturitions is not missing then the number of micturitions for that day is considered to be the number of micturitions during the daytime.
- both daytime and nighttime micturitions are missing then the number of micturitions for that day is considered missing.
 - If for a weekend day (Saturday Sunday):
- No pee volume is recorded for Saturday or for Sunday then the number of micturitions is missing for Saturday or Sunday, respectively.
- No pee volume is recorded for Saturday and for Sunday then the number of micturitions is missing for both days.

If the wake-up time is the same as the time of micturition, then the micturition will be counted as a nighttime micturition.

Note: the first micturition occurring at or after the time of wake-up is considered a nighttime micturition.

A micturition episode is counted as micturition regardless of whether volume voided was recorded or not.

A micturition will also be counted if the subject assessed an episode as both micturition and incontinence (leakage).

If data of more than 7 days prior to a visit is available, only the last 7 days prior to the visit will be used for the analysis.

The baseline will be defined by the micturitions results obtained from the diary 7 days prior to visit 3/week 0 (baseline).

The visit 7/week 12/EoT visit will be defined as the subject's value at week 12 or in case of missing week 12 data, the last available result post-baseline.

Subjects without baseline or any post-baseline value will not be included in the change from baseline calculation although they will be included in the summary for either baseline or any post-baseline visit whichever timepoint the data is available.

Change from baseline to visit 7/week 12/EoT is defined as:

Result at visit 7/week 12/EoT – Result at baseline (visit 3/week 0).

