5.2.4 Mean Number of Daytime Micturitions per 24 hours

For a week day the daytime micturitions will be derived from "Number of Times using the Toilet During the Day" was entered into the 5-day Week Diary.

For a weekend day the daytime micturitions will be derived from the number of times a "Pee in Toilet" or a "Pee in Toilet and Leakage" was entered into the 2-day Weekend Episodic Diary between the time the subject woke-up (exclusive) and went to sleep (inclusive). However, the first micturition occurring at or after the time of wake-up it is considered a nighttime micturition, see Section 5.1.

The total number of micturitions per weekend day is equal to the total number of times, in the diary, an amount of pee was recorded during daytime for that day.

For each subject, the mean number of daytime micturitions at Visit x (x=4, 5, 6, and 7) in the week before the visit will be calculated as:

Sum of the Number of Daytime Micturitions (per day) over the Valid Diary Days prior to Visit x Number of Valid Diary Days

5.2.5 Number of Dry (incontinence free) Days per 7 Days at the End of the 12-weeks Treatment Period

For a week day a "Dry (incontinence free) Day" is defined as a day where the response is "Dry" to the question "How was your Day" and to "How was your Night".

Let D_{dry} be the number of valid diary days where the response to both questions was "Dry". Let D_{wet} be the number of valid diary days where the response to one of the two questions or to both questions was "Wet".

For a weekend day a "Dry (incontinence free) Day" is defined as a day where no "Leakage" and no "Pee in toilet and leakage" are reported. A "Wet (incontinence) Day" is defined as a day where a "Leakage" or a "Pee in toilet and leakage" is reported.

If $(D_{dry} + D_{wet}) > 3$, then the number of dry days per 7 days at Visit 7 will be calculated for a subject as:

 $\frac{D_{dry}}{(D_{dry}+D_{wet})} \times 7$, otherwise its value is missing.

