6.4.1.1 Primary Analysis for Primary Efficacy Endpoint

The primary estimator for the primary estimand as defined in Section [2.1.1 Estimand] will be calculated according to the evaluation of the primary efficacy endpoint. The primary efficacy endpoint will be analyzed using an analysis of covariance (ANCOVA). The ANCOVA model will include treatment group, sex and geographical region as fixed effects and the mean number of micturitions per 24 hours at baseline as covariate. This analysis will be performed with imputation of missing visit 7/week 12 data using the last observation carried forward (LOCF) method.

The hypothesis for comparisons is given as follows:

- H₀: The adjusted mean change from baseline at visit 7/week 12 in mean number of micturitions per 24 hours for mirabegron and placebo are the same.
- H1: The adjusted mean change from baseline at visit 7/week 12 in mean number of micturitions per 24 hours for mirabegron and placebo are not the same.

Statistical testing will be done 2-sided at a 10% significance level. A 90% CI for the treatment difference (mirabegron – placebo) will be provided. The primary analysis will use the FAS. The plausibility of the underlying assumption of missing at random for the primary estimator will be evaluated and, therefore, the estimation of the treatment effect.

The ANCOVA model results will be presented with least squares (LS) means and two-sided 90% confidence intervals (CIs) for mean changes from baseline within each treatment group. Differences in LS means between mirabegron versus placebo will be derived and presented together with two-sided 90% CIs. T-statistics corresponding to the Type III sums of squares for the differences in the LS means will be used to obtain p-values for the comparisons.

Model fitting will be visually assessed. A scatter plot of residuals versus predicted values, along with histogram and normal probability plots will be produced.

Sensitivity analyses under alternative assumptions for missing data mechanisms such as missing not at random to show robustness of the estimates will be further specified.

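### The primary endpoint scores a weekday with only its daytime or only its nighttime count as a full 24-hour day; separately, one weekend sentence contradicts the entry-based count

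*SAP*

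**What the plan says.** **Weekdays.** The SAP 5.1 notes deal with a weekday that has one of its two counts. With the daytime count missing, "then the number of micturitions for that day is considered to be the number of micturitions during the nighttime". The mirror case, where "the number of nighttime micturitions is missing but the number of daytime micturitions is not missing", takes the daytime count as the day's total. A weekday is set to missing only when both counts are absent. SAP 5 says a valid weekday for micturitions "is any diary day for which the response to the question 'Number of times using the toilet during the day/night' is not missing". The visit mean is the sum of the 24-hour counts over valid days divided by the number of valid days, with at least 4 and at most 7.

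**Weekends.** SAP 5.1 first counts diary entries for urinating in the toilet, with or without leakage, and splits them into day and night by sleep and wake times. It then says the weekend total is the number of times "an amount of pee was recorded during daytime and nighttime for that day". A later note in the same section says: "A micturition episode is counted as micturition regardless of whether volume voided was recorded or not". SAP 5.2.4 repeats the amount-based sentence for daytime voids ("an amount of pee was recorded during daytime for that day").

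**The concern.** A half-completed weekday adds only part of its voids to the numerator but a whole day to the denominator. That is the same as imputing zero for the missing half. The visit mean is too low whenever the missing half contained a void, and the error is large mainly when the daytime half is missing.

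At week 12 the error looks like improvement; at baseline it looks like worsening. If half-days are equally common in both arms, the main result is noise, and the contrast also shrinks if the drug acts on daytime voids. If they are more common in one arm, the treatment comparison is biased. The interim futility calculation in SAP 6.9 uses the same ANCOVA and so inherits the rule.

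The weekend conflict is a smaller and separate matter. Two programmers following SAP 5.1 could derive different values for the same diary if some entries lack a volume.

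**Working it through.** **Plan's own figure.** Inputs from SAP 3: difference 0.9, SD 2.3, 82 evaluable children per arm, two-sided alpha 0.10. The standard error is 2.3 × √(2/82) = 0.359, so the noncentrality is 0.9/0.359 = 2.51. The noncentral t with 162 degrees of freedom gives 80.2% power. The plan's 80% is reproduced and is not in dispute.

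**Effect on one child.** The documents give no day/night split. Assume d = 6 to 8 daytime voids and 1 night void.

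- One weekday without its daytime half: 6/7 = 0.86 to 8/7 = 1.14 with 7 valid days; 6/4 = 1.5 to 8/4 = 2.0 with 4 valid days.
- One weekday without its night half: 1/7 = 0.14 or 1/4 = 0.25.

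**Equal rates in both arms, week 12 only.** Let p be the share of weekdays without the daytime half, with 5 weekdays in a 7-day diary. The added variance is v = 5p(1−p)(d/7)², and the new SD is √(2.3² + v). If, in the extreme case, the whole effect lies in daytime voids, the contrast also becomes 0.9 × (1 − 5p/7).

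| p | d | v | SD | Power, noise only | Contrast if effect all daytime | Power, noise and shrinkage |
|---|---|---|---|---|---|---|
| 2% | 6 | 0.072 | 2.316 | 79.8% | 0.887 | 78.8% |
| 2% | 8 | 0.128 | 2.328 | 79.4% | 0.887 | 78.4% |
| 5% | 6 | 0.174 | 2.338 | 79.1% | 0.868 | 76.5% |
| 5% | 8 | 0.310 | 2.366 | 78.2% | 0.868 | 75.6% |
| 10% | 6 | 0.331 | 2.371 | 78.1% | 0.836 | 72.7% |
| 10% | 8 | 0.588 | 2.424 | 76.5% | 0.836 | 71.0% |

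A simulation of the last column (20,000 trials per cell) agreed to within 0.8 of a point. If baseline is affected as well, with an assumed ANCOVA slope of 0.5 and no shrinkage, noise-only power is 79.7%, 78.8% and 77.6% for d = 6, and 79.2%, 77.7% and 75.6% for d = 8.

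**Unequal rates.** Assume an error of 1.0 per affected child at week 12. A gap between arms of 5, 10 or 20 percentage points in affected children moves the contrast by 0.05, 0.10 or 0.20. By the normal approximation (80.5% to start), power falls to 76.5%, 72.0% or 61.9% if the shift works against mirabegron. One-sided type I error rises from 5% to 6.6%, 8.6% or 13.8% if it favours mirabegron.

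**Entry threshold.** Protocol 5.1, criterion 15, requires a mean of at least 8. A child with 8 day voids and 1 night void, and one missing daytime half, scores (6 × 9 + 1)/7 = 7.86. With 1 night void and one such day, a child reaches 8 only if the true mean is at least (56 − 1)/6 = 9.17. This matters only if eligibility is scored by the SAP rule, which the documents do not say.

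**Planned analyses.** SAP 6.4.1.3 varies the analysis set, the imputation of missing visits, the model and the use of ranks. All of these start from the same visit means, and multiple imputation acts only on missing visit values, which a half-day is not.

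**Weekends.** Take 8 entries every day, with 1, 2 or 3 per weekend day lacking a volume. Counting entries gives 8.00. Counting recorded amounts gives (40 + 14)/7 = 7.71, (40 + 12)/7 = 7.43 or (40 + 10)/7 = 7.14.

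**The case against.** The strongest counter-reading is that the valid-day definition in SAP 5 speaks of the day/night response and could require both parts, so that a half-day never enters the mean. The wording is ambiguous, but on that reading the half-day notes in SAP 5.1 would have nothing to do. The natural reading is that one half suffices.

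Second, the size rests on assumed rates, and nothing suggests that rates differ by arm in a double-blind trial. That stands. At 2% of weekdays the noise costs 0.4 to 0.8 of a power point, and the 71.0% needs three unfavourable assumptions together. The SD of 2.3 comes from another trial and may already include some diary noise, so the losses may be overstated.

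Third, the plan has safeguards: the practice diary (Protocol 7.1.1), diary review before visits (Protocol 7.6), the quality tolerance limit on missing micturition counts (Protocol 12.2.4, Table 9), the deviation category for missed primary assessments (SAP 6.2.2), case-by-case per-protocol exclusion (SAP 4.5.1), the rank analysis with the Hodges-Lehmann estimate (SAP 6.4.1.3.4), and an optional outlier analysis (SAP 6.10.3). These may make half-days rarer or dampen their effect. None changes how one is scored.

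Fourth, the weekend point is largely editorial, because the explicit note that a volume is not needed should govern. That is fair. It is a wording repair and adds no weight to the weekday point.

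**Conclusion.** The concern holds. The weekday rule is wrong as written: it turns a missing count into zero voids within the primary endpoint. Confidence is high on the reading of the rule; the practical impact is unknown, because the documents give neither a half-day rate nor a day/night split.

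For one child the error can equal the planned effect. For the trial as a whole it is modest if half-days are uncommon and balanced between arms, and larger if they are frequent or unbalanced. The entry-threshold effect is conditional. The weekend conflict is real but confined to one sentence and its repeat. This should be fixed before database lock; it does not invalidate the design or change the sample size.

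The SAP already applies a stricter principle elsewhere. For dry days (5.2.5) a weekday is dry only if both halves are dry and wet if either is wet, so a day with one dry half and one missing half is neither.

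**What to change.** 1. In SAP 5 and 5.1, make a weekday valid for the 24-hour count only if both the daytime and nighttime counts are present. Otherwise set the day to missing under the existing rule of at least 4 valid days, at baseline and at every later visit.
2. Report partly completed weekdays by arm and visit.
3. Run the current half-day scoring as a sensitivity analysis.
4. Delete the amount-based sentence in 5.1 and its repeat in 5.2.4, so that weekend days count every toilet entry, with or without leakage. The requirement of at least one volume for a valid weekend day can stand alongside this. If it is dropped for micturitions, replace it with a stated minimum of one toilet entry and keep it for the volume endpoints.
5. Section 5.2.4 divides daytime voids by the number of valid diary days, so state there which weekdays count in that denominator.

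The cost is SAP wording, derivation code, one table and one extra run. The drawback is that some diaries will drop below 4 valid days. A lost week 12 value then falls under "imputation of missing visit 7/week 12 data using the last observation carried forward (LOCF) method", and a lost baseline removes the child from the change analysis ("Subjects without baseline or any post-baseline value will not be included in the change from baseline calculation"). The rule also discards days that lack only the night count, where the error is small. Setting a day to missing only when its daytime count is absent would lose fewer days but leave that small error in place. The sensitivity run shows whether the choice matters.

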3.1 Estimand

The estimand of most clinical importance for this study is defined by the following 4 attributes:

- Target population: all children who took at least 1 dose of the study drug, and in whom a nonmissing measurement for micturition frequency at baseline and after administration of the study drug is available
- Outcome measurement: micturition frequency/day (24 hours)
- Intercurrent events:
 - 1. Discontinuation from treatment (if week 12/EoT not obtained)
 - 2. AE UTI (if occurred in week 12/EoT)

Sponsor: APGD ISN/Protocol: 178-CL-204

EudraCT number 2016-001767-37

- CONFIDENTIAL -

3. Other muscarinic antagonists or botulinum toxin see [Appendix 12.6 List of Excluded Concomitant Medications]) (if taken during the last 2 weeks prior to week 12/EoT assessment); in all cases, a hypothetical strategy will be applied

• Population-based summary: Change from baseline to week 12/EoT in micturition frequency/day (= primary endpoint, primary estimator), compared to placebo

For this placebo-controlled study, this "de jure" estimand chosen is considered the appropriate choice. As some effect is expected early in the study and with continued treatment could be expected to be maintained, it's considered appropriate to impute for subjects with missing values at visit 7/week 12/EoT by their last recorded post baseline visit value prior to it. This strategy also assumes that the responses after the intercurrent event would be same as for patients continuing on their respective treatment.

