9.4.1 Analysis of Primary Endpoint

9.4.1.1 Primary Analysis

The primary estimator for the primary estimand as defined in [Section 3.1 Estimand] will be calculated according to the evaluation of the primary efficacy endpoint. The primary efficacy endpoint change from baseline to week 12/EoT in mean micturitions per 24 hours (in children [5 to < 12 years of age]), will be analyzed using an analysis of covariance (ANCOVA). The ANCOVA model will include treatment group, sex and geographical region as fixed effects and the mean number of micturitions per 24 hours at baseline as covariate. This analysis will be performed and once with imputation of missing week 12 data using the last observation carried forward (LOCF) method.

The hypothesis for comparisons is given as follows:

H0: The adjusted mean change from baseline at week 12 in mean number of micturitions per 24 hours for mirabegron and placebo are the same.

H1: The adjusted mean change from baseline at week 12 in mean number of micturitions per 24 hours for mirabegron and placebo are not the same.

Statistical testing will be done at a 2-sided 0.1 significance level. A 90% CI for the treatment difference (mirabegron – placebo) will be provided. The primary analysis will use the FAS. The plausibility of the underlying assumption of missing at random for the primary estimator will be evaluated, and; therefore, the estimation of the treatment effect. Sensitivity analyses under alternative assumptions for missing data mechanisms such as missing not at random to show robustness of the estimates will be further specified in the SAP.

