9.11 Additional Conventions

Missing data for efficacy endpoints will be imputed as EoT values, details will be described in the SAP. Handling of incomplete dates will also be described in the SAP.

Geographical regions that do not enroll sufficient subjects to allow estimation of the geographical effect will be pooled for analyses by geographical region. The pooling decisions will be made and documented prior to study hardlock.

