2.1.1 Estimand

The estimand of most clinical importance for this study is defined by the following four attributes:

- Target population: all children who took at least 1 dose of the study drug, and in whom a non-missing measurement for micturition frequency at baseline and after administration of the study drug is available
- Outcome measurement: micturition frequency/day (24 hours)
- Intercurrent events:
 - 1. Discontinuation from treatment (if week 12/EoT not obtained)
 - 2. AE Urinary Tract Infection (UTI) (if occurred in week 12/EoT)
 - 3. Other muscarinic antagonists or botulinum toxin (if taken during the last 2 weeks prior to week 12/EoT assessment);

In all cases, a hypothetical strategy will be applied.

• Population-based summary: Change from baseline to week 12/EoT in micturition frequency/day (= primary endpoint, primary estimator), compared to placebo.

For this placebo-controlled study, this "de jure" estimand is considered the appropriate choice. As some effect is expected early in the study and with continued treatment could be expected to be maintained, it is considered appropriate to impute for subjects with missing values at visit 7/week 12/EoT by their last recorded post baseline visit value prior to it. This strategy also assumes that the responses after the intercurrent event would be same as for those patients continuing on their respective treatment.

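### The hypothetical strategy declared for week-12 UTI and for late antimuscarinic or botulinum toxin use has no derivation step, so an affected but obtained week-12 diary is analysed as observed

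*SAP*

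**What the plan says.** **Estimand.** SAP 2.1.1 lists three intercurrent events. The first is discontinuation with no week-12 value. The second is "AE Urinary Tract Infection (UTI) (if occurred in week 12/EoT", and the third is "Other muscarinic antagonists or botulinum toxin (if taken during the last 2 weeks prior to week 12/EoT assessment". It then states: "In all cases, a hypothetical strategy will be applied". Protocol 3.1 says the same: "in all cases, a hypothetical strategy will be applied". SAP 6.4.1.1 presents the primary analysis as the estimator for this estimand.

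**Derivation.** SAP 5.1 defines the endpoint value as the subject's "value at week 12 or in case of missing week 12 data, the last available result post-baseline". SAP 6.4.1.1 runs the ANCOVA "with imputation of missing visit 7/week 12 data using the last observation carried forward (LOCF) method", and protocol 9.4.1.1 likewise provides for "imputation of missing week 12 data using the last observation carried forward (LOCF) method".

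**Diary validity.** Under SAP 5 a diary counts for a visit if it has at least 4 valid days. SAP 6.10.1 assigns diaries to visits by date. Neither rule refers to intercurrent events, and the Outliers section (SAP 6.10.3) retains all values.

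**The concern.** The estimand asks what week-12 frequency would have been without the UTI or the other bladder drug. The derivation replaces a value only when none was obtained. Neither event makes a diary missing, and the stopping criteria in protocol 8.1 name neither, so an affected child can stay on treatment and supply a valid week-12 diary. That diary is then used unchanged. This is treatment-policy handling where a hypothetical strategy was declared.

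What is at stake is whether the prespecified estimator targets the prespecified estimand. For affected children it does not. The gap also leaves a handling decision to be made late in the trial.

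**Working it through.** **1. Event by event.**

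| Event | Declared strategy | Operative rule | Outcome |
|---|---|---|---|
| Discontinuation, week 12 not obtained | Hypothetical | LOCF (SAP 5.1, 6.4.1.1) | Has a step |
| UTI in week 12/EoT | Hypothetical | None if the diary was obtained | Used as observed |
| Antimuscarinic or botulinum toxin in last 2 weeks | Hypothetical | None if the diary was obtained | Used as observed |

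**2. Other analyses.**
- The repeated-measures model (SAP 6.4.1.3.3) has no event rule.
- Both multiple-imputation (MI) analyses (SAP 6.4.1.3.5) impute missing data only.
- The futility calculation (SAP 6.9, 9.5) uses the ANCOVA of SAP 6.4.1.1 and so the same input.
- The per protocol set (SAP 4.5.1) removes users of prohibited medication, but as whole subjects and only as a sensitivity set. It lists no UTI criterion.
- The UTI interaction (SAP 6.4.1.5) counts a UTI at any time in the trial.

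**3. The plan's own power figure.** Inputs from SAP 3 and 6.4.1.1: difference 0.9, SD 2.3, 82 evaluable per arm, two-sided alpha 0.10.
- SE = 2.3 × √(2/82) = 0.3592
- Power = Φ(0.9/0.3592 − 1.645) = 80.5%, which agrees with the stated 80%.

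**4. One affected child, no rate assumed.** A displacement of x voids a day moves that arm's mean by x/82.
- x = 1: 0.012, or 0.012/0.3592 = 0.03 SE
- x = 2: 0.024, or 0.07 SE
- x = 3: 0.037, or 0.10 SE

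**5. Illustrations.** The documents give no event rates. Rates of 2%, 5% and 10% are assumptions; they correspond to about 1.6, 4.1 and 8.2 of 82 children. Differences are written as benefit, so positive favours mirabegron.

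(a) Antimuscarinic use on placebo only, assumed effect 0.8 voids a day, SD held at 2.3: d = 0.9 − 0.8p.

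(b) UTI on mirabegron only, assumed rise of 2 voids a day: d = 0.9 − 2p. The mirabegron variance becomes 2.3² + 4p(1 − p).

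(c) UTI at the same rate in both arms, rise of 2: d stays at 0.90. Both variances become 2.3² + 4p(1 − p).

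| Assumed rate p | (a) d, power | (b) d, power | (c) d, power |
|---|---|---|---|
| 2% | 0.884, 79.3% | 0.86, about 77% | 0.90, about 80% |
| 5% | 0.86, 77.3% | 0.80, about 71% | 0.90, about 79% |
| 10% | 0.82, 73.8% | 0.70, about 61% | 0.90, about 78% |

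Reversing (b), with UTI in 2% of placebo only, gives d = 0.94 and power of 83.2%. The direction therefore depends on which arm has more events.

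**The case against.** The strongest reply is that the intent is clear. SAP 2.1.1 goes straight from the hypothetical strategy to imputation, and it assumes that responses after an event match those of patients continuing treatment. A statistician could infer that affected values are to be treated as missing. That is a fair reading of intent, but it is an assumption and not an instruction. The imputation sentence there covers only subjects with missing values, and a programmer following SAP 5.1 would keep the observed diary.

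Second, safeguards exist for the medication event. These drugs are prohibited (protocol 6.5 and Appendix 12.6), their use is major deviation PD4, and the per protocol set drops users and is analysed with and without LOCF. This stands in part: for that event alone the gap is close to one of wording. It does not help with UTI. The classification meeting could add a UTI exclusion, but none is written.

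Third, the numerical effect may be very small. That stands. A reader might infer from the 61% figure that the trial is underpowered or its result biased in a known direction. The documents do not support this, because that case assumes both a 10% rate and complete imbalance between arms. A reader might also take the 0.8 propiverine difference in SAP 3 as a ceiling for event 3. It is one drug's observed difference against placebo, used here as a single assumed value, and says nothing about the other antimuscarinics or botulinum toxin.

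**Conclusion.** The gap is certain from the text. The declared strategy for these two events is not carried out by any rule in either document, and following SAP 5.1 exactly contradicts it. UTI is the weaker point, since nothing planned isolates or removes week-12 UTI values.

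Size and direction are unknown without event rates. If events are rare or balanced, the effect on the estimate and on power is probably small; the larger losses need common and unbalanced events. All power figures rest on the assumed rates and displacements above, with 82 children per arm and SD 2.3. The reason to act is agreement between estimator and estimand, not a demonstrated threat to the result. This should be fixed, and SAP section 1 allows revision until database hard lock.

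**What to change.** In SAP 5.1 and 6.4.1.1, before imputation, set the week-12 diary value to missing when either event applies and carry forward the last unaffected post-baseline diary. State also:

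- **UTI flag:** the adverse event dates overlap the week-12 diary days.
- **Uncertain dates:** cases with missing or imputed event onset or end dates, or medication dates, are decided blinded at the classification meeting. This matters because SAP 6.10.2.2 gives onset rules only, and SAP 6.10.2.3 can set a medication stop date to the end of 2099.
- **No unaffected diary:** the child stays in the full analysis set, has no LOCF change value, is included in the MI analyses, and is counted by arm.
- **Same input elsewhere:** use it in the repeated-measures and MI analyses, and in the futility analysis only if that has not yet been run.
- **As-observed analysis:** report it as supplementary.

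The basis for doing this in the SAP is that it carries out the strategy already declared in protocol 3.1. A reader might cite protocol 9.11 instead, but it says "Missing data for efficacy endpoints will be imputed as EoT values, details will be described in the SAP"; that covers missing data and does not by itself authorise setting aside obtained values.

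The alternative is to change the declared strategy for these two events in protocol 3.1, its synopsis copy and SAP 2.1.1, which requires a protocol amendment.

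The recommended route costs SAP wording and a flag programmed from adverse event and concomitant medication dates already collected. The downside is a few more carried-forward week-12 values and possibly a child with no LOCF value.
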